3.2.2 Secondary Objectives

1. Determine the clinical outcomes between groups.
2. Distinguish extravasation post closure at the end of the procedure.
3. Compare the need for open vascular surgery between groups.

4. Examine PTA or Stents to the CFA to help hemostasis or local vascular complications between groups.
5. Number of Perclose devices used between groups.
6. Compare Bleeding/Hematoma between groups.
7. Examine the difference in hospital length of stay between groups.
8. Examine renal function post procedure
9. Difference in pain or numbness in the distal extremity between groups
10. Mortality related to complications from vascular closure site between groups.
11. Conversion to general anesthesia due to additional procedures required to address the CFA access site complications between groups.

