3.3 Study Duration

We plan to enroll up to a total of 100 patients, 50 patients in each group. The total study duration will be approximately 12 months post IRB approval and study initiation. We will follow patients for 3 months post procedure for any adverse events; however, we would expect to see them within 3 days if there are events to occur.

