3.4 Selection of Study Participants & Informed Consent

Patients at the UT Medical Center who meet the predefined inclusion and exclusion criteria will be enrolled after they provide consent to participate. The nature and purpose of the study will be explained to the patient by one of the investigators and the patient will be given a copy of the informed consent to review. The investigator or study coordinator will answer any questions which the patient may have prior to their signing the consent. The signed informed consent will be kept in the patient's research chart and a copy will be given to the patient. No study related interventions will be performed until after the patient signs the informed consent. The consent process will occur at an earlier date than the actual procedure to give patients plenty of time to review and ask questions.

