5. RISK

5.1 Physical Risks

Although the procedure approach being used in this protocol has been well tested for efficacy and safety, there may be potential risks associated with participation. Any medical treatment can have temporary and permanent side effects and can cause unforeseen adverse reactions, intolerance, or worsening of co-morbidities, which could lead to acute adverse event such as worsening kidney disease, allergic/immunologic reaction, infections, vascular complications, stroke, or death. All of which are risks associated with the TAVR procedure itself and are of low probability and discussed in detail prior to the TAVR procedure. With any invasive procedure, there may be unforeseeable risks associated with the procedure resulting in complications or physical harm. Any subject with known medical conditions, or on a concurrent medication in which the study intervention is not recommended, will be excluded from participation.

The intervention used in this study are currently in common use and will be administered in accordance with current standards (ultrasound and fluoroscopy-guided vascular access, modified Seldinger technique) which are put forth in attempts to mitigate any potential risks. Patients will be carefully screened for contraindications to participation prior to study enrollment. We will monitor for adverse events in enrolled patients.

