7. ENDPOINTS/OUTCOMES

7.1 Efficacy

1. Evaluate for contrast extravasation post closure of femoral artery at the end of the procedure
2. Determine need for Vascular surgery consultation
3. If vascular complication, was PTA, stenting, or open surgery used
4. Number of perclose devices used to close the femoral artery access site
5. Determine presence of other vascular complications i.e. bleeding, hematoma, emboli etc.
6. Review lab values and vital signs to determine if there is any clinical deterioration (drop in hemoglobin, worsening of creatinine, development of hypotension/shock, infections/sepsis)
7. Determine if there is a difference between hospital length of stay
8. Assess for difference in pain/numbness in distal extremities post-procedure
9. Assess for differences in mortality related to complications between the groups
10. Failure of treatment

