differences at baseline will be accounted for in the primary analysis using logistic regression. Chi-square or Fisher's Exact test will be performed to compare the treatment arms on distinguishing extravasation post-closure at the end of the procedure (yes/no), comparing the need for open vascular surgery (yes/no), utilizing a PTA/stent to help with hemostasis or local vascular complications (yes/no), bleeding/hematomas (yes/no), pain or numbness in the distal extremity (yes/no), mortality related to complications associated with the vascular closure site (yes/no), and conversion to general anesthesia due to additional procedures required to address CFA access site complications (yes/no). Cross-tabulation tables with frequencies, percentages, and associated OR with 95% CI will be reported and interpreted for all bivariate analyses of categorical, secondary outcomes. For count variables and non-normal continuous parameters (number of perclose devices, LOS, and serum creatinine), Mann-Whitney U tests will be performed to compare the two treatment arms. Medians and interquartile ranges will be reported and interpreted for the non-parametric analyses of the count and continuous parameters. Survival analysis will be performed using Kaplan-Meier in order to compare the two treatment arms on "time-to-event" outcomes. Mean and median times to events will be presented. Log-rank, Breslow, and Tarone-Ware tests will be used to compare the respective groups. Survival plots will also be graphed. All analyses will be performed using SPSS Version 29 (Armonk, NY: IBM Corp.) and statistical significance will be assumed at an alpha value of 0.05.

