11.2 Data and Safety Monitoring

Monitoring will be completed by the GSM Office of Research Support and/or The Office of Clinical Trials and include a review of original case records. It will include monitoring to assess patient safety, the consent process, record-keeping, protocol adherence, and data collection. The Investigator will record all protocol deviations. Unexpected clinically significant adverse events will be reported to the IRB. In general, the investigators will monitor any adverse reaction to study procedures conducted during the study. Any missing data will be omitted from the final statistical analysis.

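### Length of stay goes into a Mann-Whitney test with no defined start and no rule for death before discharge, so an early death could rank as a favourable short stay

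*Combined protocol and SAP*

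**What the plan says.** Section 9.2 (Statistical Methods) states that for "count variables and non-normal continuous parameters (number of perclose devices, LOS, and serum creatinine), Mann-Whitney U tests will be performed", and reports medians and interquartile ranges. The variable appears as item 7 of the eleven secondary objectives in Section 3.2.2 ("Examine the difference in hospital length of stay between groups"), as item 7 of the efficacy list in Section 7.1 ("Determine if there is a difference between hospital length of stay"), and as a recorded item in Section 4.2. None of these gives a start point, an end point or a rule for death in hospital.

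Four other statements bear on the point:
- Section 9.2 has a separate yes/no comparison, but only of "mortality related to complications associated with the vascular closure site (yes/no").
- Section 9.2 promises intention-to-treat for all inferential analyses. It also plans Kaplan-Meier analyses of time-to-event outcomes that it does not name.
- Section 11.2: "Any missing data will be omitted from the final statistical analysis".
- On the timing of adverse events, Section 3.3 says "we would expect to see them within 3 days if there are events to occur".

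**The concern.** In a comparison of hospital stay, shorter is taken as better. A patient who dies soon after the procedure has a short stay, so ranking observed days credits the death to the arm in which it occurred. That is the wrong direction for a trial about access complications, some of which can be fatal: death is among the listed device risks in Section 5.2.

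The start of the clock is also open. If it runs from admission, any inpatient days before the valve procedure enter the outcome although neither arm can affect them.

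Both choices would otherwise be made after the data are seen. At stake is the reading of one secondary endpoint, not the primary result.

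**Working it through.** **Plan inputs.** 50 patients per arm (Sections 3.3 and 9.1), two-sided testing (9.1), alpha 0.05 and the Mann-Whitney test (9.2). The plan has no length-of-stay figure to reproduce: its sample size calculation concerns access site complications, and it gives no expected stay, spread or death rate.

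**Step 1: what could happen to a death under the text.**
- Ranked as observed: the interval to death is a recorded number, so it enters the test as a short stay.
- Omitted as missing: Section 11.2 does not say that a stay ended by death is missing. If it were dropped, stay would be compared among survivors only, which sits badly with the intention-to-treat commitment.
- Handled elsewhere: the mortality outcome covers only closure-site deaths, and Kaplan-Meier is not tied to discharge.

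Each route leaves a rule to be written.

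**Step 2: size per death, observed days against worst rank.** Let P be the Mann-Whitney probability that a patient in one arm stays longer than a patient in the other, counting ties as one half. Without ties its null standard error is √[(50+50+1)/(12×50×50)] = √(101/30,000) = 0.0580.

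Assume 30% of patients stay more than 1 day and the other 70% exactly 1 day, ignoring ties among the longer stays. The tie correction is 1 − (70³−70)/(100³−100) = 0.657, so the standard error is 0.0580×√0.657 = 0.0470. Moving one death to the worst rank changes P by (1 − share of the other arm beaten, ties half)/50:

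| Death scored at | Change in P | Change in z |
|---|---|---|
| 0.5 day (below all) | 1/50 = 0.020 | 0.020/0.0470 = 0.43 |
| 1 day (tied with 70%) | (1−0.35)/50 = 0.013 | 0.013/0.0470 = 0.28 |
| 2 days or later | at most 0.30/50 = 0.006 | at most 0.006/0.0470 = 0.13 |

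If 20% or 40% stay more than 1 day, the first row becomes 0.49 or 0.39 and the second 0.30 or 0.27. From day 2 on, the death already outranks at least 70% of the other arm, so it counts as unfavourable even when scored as observed.

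**Step 3: effect on power.** Simulation, 2,000 runs per case, 50 per arm. Assumed stay: lognormal, median parameter 1.7 days, log-SD 0.6, rounded up to whole days. The lithotripsy (IVL) arm has a true benefit of −0.35 on the log scale. Raw scoring here puts each death below every survivor, the extreme case.

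| Early deaths | Power, raw | Power, worst rank |
|---|---|---|
| none | 76% | 76% |
| 1 control | 68% | 79% |
| 2 control | 59% | 84% |
| 3 control | 51% | 88% |
| 3 IVL | 88% | 50% |

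The last row shows the harmful direction: three deaths in the treated arm raise the chance of declaring a shorter stay.

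**Step 4: can the scoring reverse the result?** Without ties, the distance from no effect to significance is 1.96×0.0580 = 0.114. At 0.02 per death, 0.114/0.02 = 5.7, so about 6 net deaths in one arm are needed for scoring alone to span it. In the benefit case P is 0.356 and each control death scored raw moves it about 0.013 toward 0.5. Changing the sign takes (0.5−0.356)/0.013, about 11 deaths.

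**Step 5: pre-procedure days, if counted.** Same simulation, with 1 to 7 extra days given at random to 10%, 20% or 30% of both arms. Power falls from 77% in that set of runs to 61%, 45% and 36%. Under no effect, rejection stays at 5.2%, 5.6% and 4.7% and P stays at 0.50.

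**The case against.** A reader might infer that the plan awards deaths the best rank, counts days before the procedure, and so can report the reverse of the truth. The documents do not support that:
- They never describe the stay as total or as running from admission. No section says that any participant is an inpatient before the procedure day; "The consent process will occur at an earlier date than the actual procedure" settles nothing about admission.
- They do not say how a death is scored. Omission under Section 11.2 is another reading, with a different fault.
- Section 5.1 says of the listed risks, death included, "All of which are risks associated with the TAVR procedure itself and are of low probability". The 6 to 11 net deaths of Step 4 are not what the plan anticipates.
- Section 3.3 expects events within 3 days, not only on day 0 or 1, and a death on day 2 or 3 has little effect.
- Deaths are not hidden: Section 4.2 records mortality, Section 9.2 compares closure-site deaths, and Section 7.2 counts related serious adverse events.

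All of this stands and limits the point. It does not close the gap. Both clock and death rule are still undefined, and the tested mortality outcome leaves out in-hospital deaths from other causes. It is also fair that worst rank is one accepted method among several; time to live discharge with death as a competing event is another.

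**Conclusion.** The point holds as a gap in definition. Length of stay is sent to a rank test without a start point or a rule for death before discharge. If observed days are ranked, each death on day 0 or 1 shifts z by about 0.3 to 0.4 toward its own arm relative to worst rank, and each death on day 2 or 3 by about 0.1. A few early deaths in one arm can distort or bury a difference; one or two would reverse only a difference near zero. Pre-procedure days, if counted, dilute the comparison without directional bias, because randomisation balances them in expectation. Chance imbalance at 50 per arm remains possible.

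The sizes depend on the assumed stay distribution, the assumed number and timing of deaths, and the assumed share of patients with earlier inpatient days. The endpoint is one of eleven secondary objectives in a self-declared pilot, so this is a minor improvement.

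**What to change.** Add to Section 9.2: length of stay is the number of days from the TAVR procedure to live discharge. Patients who die before discharge receive the worst rank in the Mann-Whitney test. The number of such deaths is reported by arm beside the result, whatever their cause, and length of stay among survivors is given as a descriptive supplement.

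The cost is one or two sentences. Section 4.2 already collects procedure reports, discharge summaries and mortality, from which the dates can be taken. The downside is that the comparison becomes a composite of stay and survival, which is why the deaths and the survivor summary should stand beside it.

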4. STUDY PROCEDURES

4.1 Screening and Enrollment

Screening assessments will be completed by the study team on a day before the procedure to allow patients time to review and ask questions. Assessments will be initiated after the Informed Consent Form (ICF) Process. A study designee will present the study information to the patient. They will explain the purpose, risk, and benefits to the subject and present them with an IRB approved ICF. The potential participant will be given ample time to read the ICF and all questions and concerns from the subject will be addressed by a study team member. No procedures will be initiated prior to the subject signing and dating the ICF. After the subject signs the ICF, a copy will be given to them for their records. Participants will be informed that they can decline participation in the study without any effect on their health care. They can also withdraw their consent, including the consent to do various screening tests, at any time.

4.2 Datapoints/procedures to be collected/obtained:

- Informed Consent
- Medical History Review for Inclusion/Exclusion Criteria
- Concurrent Medication Review
- Pre-TAVR CT scan review
- Review of pre procedure laboratory results
- Demographics
- Pre-procedure consultation/progress notes
- Post procedure notes (consult, progress, discharge summary)
- Post procedure laboratory results and imaging
- Post discharge follow up office notes and vital signs

If subjects meet all I/E criteria, they will be Enrolled, and the following will be recorded

- Flow rates prior to and post procedures
- Documentation of extravasation post closure at the end of the procedure.
- If open vascular surgery occurred
- Number of perclose devices used

- Bleeding/Hematoma outcomes
- Hospital length of stay
- Renal function lab results post procedure
- Pain or numbness in the distal extremity post procedure
- Whether conversion to General Anesthesia was needed during procedure
- Review of post-procedure laboratory results
- Surgical/procedure reports
- Mortality
- Discharge summary
- Adverse event monitoring

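### Worsening of creatinine is an endpoint in section 7.1, but section 9.2 does not state any use of the pre-procedure value and plans no count of patients who worsened

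*Combined protocol and SAP*

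**What the plan says.** Section 7.1 item 6 lists, as signs of clinical deterioration to be looked for in laboratory values and vital signs, "drop in hemoglobin, worsening of creatinine, development of hypotension/shock, infections/sepsis". It gives no threshold and no time point. Secondary objective 8 in section 3.2.2 is looser: "Examine renal function post procedure".

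Section 4.2 collects what a within-patient comparison needs. It lists "Review of pre procedure laboratory results" and, after enrollment, post-procedure renal function results.

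Section 9.2 deals with creatinine in one place. For "non-normal continuous parameters (number of perclose devices, LOS, and serum creatinine), Mann-Whitney U tests will be performed" between the arms, and "Medians and interquartile ranges will be reported and interpreted for the non-parametric analyses of the count and continuous parameters". For the yes/no secondary outcomes, "Cross-tabulation tables with frequencies, percentages, and associated OR with 95% CI will be reported". Seven such outcomes are named: extravasation, open vascular surgery, PTA/stent, bleeding/hematoma, pain or numbness, closure-site mortality and conversion to general anesthesia. Worsening of creatinine is not among them. Baseline differences are carried into the primary analysis only.

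**The concern.** Worsening is something that happens within a patient, so it needs the pre-procedure value. A comparison of post-procedure levels answers objective 8 but not item 6 of section 7.1. Two things could be lost.

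- **Sensitivity to a general rise.** Creatinine differs widely between patients before any procedure. A rank test on the level carries all of that spread, and a test on change removes most of it when the two values are closely correlated.
- **Visibility of a few large rises.** A rise confined to a handful of 50 patients hardly moves a median or quartile. The laboratory results are on file, so a count could be made later, but its cut-off would then be chosen with the data in hand.

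Sections 5.1 and 5.2 name worsening kidney disease and renal failure as possible harms, and only one arm receives the lithotripsy device. A comparison by arm is therefore of real interest.

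**Working it through.** **Plan's own figure.** There is none for creatinine. From the plan: 50 per arm (section 9.1), two-sided alpha 0.05 (9.1 and 9.2), Mann-Whitney (9.2). Everything else below is assumed.

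**Step 1: a general rise, level against change.** Assume log-creatinine with between-patient SD 0.35 and 10% measurement noise on each value.

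- SD of the post-procedure log level = √(0.35² + 0.10²) = 0.364.
- SD of the log post/pre ratio = √(0.10² + 0.10²) = 0.141.
- Approximate power = Φ(δ / (SD × √(2/50)) − 1.96), with √(2/50) = 0.2.
- δ = 0.10 on the log scale (about a 10% rise). Level: 0.10/0.0728 = 1.37, power Φ(−0.59) = 28%. Ratio: 0.10/0.0283 = 3.54, power Φ(1.58) = 94%.
- δ = 0.15. Level: 0.15/0.0728 = 2.06, power Φ(0.10) = 54%. Ratio: power above 99%.

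Simulated Mann-Whitney power agrees: 27–54% on the level and 92–100% on change.

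The gain depends on the pre/post correlation ρ, because SD(change) = SD × √(2(1 − ρ)), which is below SD only when ρ exceeds 0.5. The inputs above imply ρ = 0.1225/0.1325 = 0.92. A separate simulation (log-SD 0.4, shift 0.15) gave 43–45% on the level, and on change 44, 66, 81 and 98% at ρ = 0.5, 0.7, 0.8 and 0.9.

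**Step 2: a rise in a few patients.** Same spread and noise, centred on 1.1 mg/dL. Injured patients rise 1.5–3 fold, with the peak on day 1, 2 or 3 with equal chance. Section 3.3 says of adverse events that "we would expect to see them within 3 days if there are events to occur". The value used is that of the first post-procedure day, unless stated, and a patient is flagged at 1.5 times the pre-procedure value. 4,000 trials per scenario.

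| Injured, worse vs other arm | Power: level / ratio / Fisher on count | Worse arm shown higher: median / upper quartile / count |
|---|---|---|
| 6% vs 2% | 5.6 / 6.6 / 0.7% | 57 / 59 / 67% |
| 10% vs 2% | 7.6 / 10.0 / 5.8% | 63 / 66 / 87% |
| 20% vs 2% | 18.8 / 31.6 / 44.3% | 79 / 86 / 99% |
| 10% vs 2%, full rise caught | 9.2 / 10.0 / 17.0% | 66 / 73 / 92% |

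At 10% vs 2%, the mean medians are 1.15 and 1.11 mg/dL, while the mean numbers flagged are 3.4 and 0.8. With 15% noise, the 87% falls to 79%.

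**Step 3: precision of a count.** Newcombe interval from Wilson limits, for 5/50 vs 1/50. The Wilson limits are 0.0435 to 0.2136 and 0.0035 to 0.1050.

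- Lower: 0.08 − √((0.10 − 0.0435)² + (0.1050 − 0.02)²) = −0.022.
- Upper: 0.08 + √((0.2136 − 0.10)² + (0.02 − 0.0035)²) = 0.195.

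So 8 points (95% CI −2.2 to 19.5), Fisher p = 0.20. The same method for 3/50 vs 1/50 gives 4 points (−5.4 to 14.3).

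**Step 4: why the window matters.** Length of stay is itself an outcome ("Examine the difference in hospital length of stay between groups"). With 10% injured in both arms and daily draws, a window closing at discharge flags 6.7% after a 1-day stay and 10.2% after a 3-day stay. That is a false difference of 10.2 − 6.7 = 3.5 points.

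**The case against.** **The endpoint may be read too strictly.** Item 6 can be taken as a bedside review with creatinine as one example, and the only objective that names renal function is met by the planned test. That has some force, but item 6 stands under the endpoints heading of section 7 and names worsening, so the analysis section should say how it will be shown.

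**A reader might infer that the plan chose raw level over change, or that its test is invalid.** The documents support neither. Section 9.2 leaves the variable unspecified, and after randomization a comparison of post-procedure values is valid. The defect is an unstated variable and a missing count.

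**A reader might infer that renal harm goes unrecorded.** It does not. Section 8 records related adverse events and documents SAEs, apart from unrelated worsening of a co-morbidity, and section 7.2 counts related events. What remains is that these counts depend on attribution and that section 9.2 tabulates none of them by arm.

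**A reader might infer that a count detects harm better.** At 10% vs 2% it does not: 6% power against 8% for the planned test on the level. The 87% against 63% contrast also favors the count by construction, because injury was simulated as a rise of at least 1.5 fold and then flagged at 1.5. This objection stands, and the count is justified as description only.

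**Conclusion.** The point holds as a minor gap. Section 7.1 makes worsening of creatinine an endpoint. Section 9.2 does not say that the pre-procedure value is used, and it plans no count of patients who worsened.

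The size depends on assumptions. For a general rise, testing change rather than level could raise power from 27–54% to 92–100% when the pre- and post-procedure values are closely correlated, with no gain at a correlation of 0.5. For rises in a few patients, the benefit is that the reader can see them; proof is out of reach with 50 per arm. The documents supply no renal injury rate, variability or draw schedule, so none of these figures predicts this trial. The primary analysis is unaffected.

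**What to change.** In section 9.2:

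1. Run the Mann-Whitney test on each patient's post/pre creatinine ratio, or on the change, instead of the raw level.
2. Report descriptively, per arm, n/N with a post-procedure value at least 1.5 times the pre-procedure value, with the risk difference and 95% CI, whatever the attribution.
3. Use routinely collected results from one prespecified window, the same in both arms and not ending at discharge. State which value counts if there are several. The first post-procedure day's value does not depend on stay, but caught only about 65% of injuries under the timing assumed above.
4. Show the number without a value per arm, because section 11.2 drops missing data.

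The cost is one definition and one table row, using data already listed in section 4.2. One cut-off and one window must be agreed; 1.5 is a proposal and is not taken from the documents. The counts will be imprecise. Not required for this point: an extra scheduled draw, a maximum through day 7, dialysis capture, or chart abstraction for shock and sepsis.

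### If serum creatinine is compared as a post-procedure level, the planned Mann-Whitney test is valid but leaves out the pre-procedure value; prespecified baseline adjustment would be a cheap gain in precision

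*Combined protocol and SAP*

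**What the plan says.** Section 9.2 groups creatinine with two other count or non-normal variables and gives one test for all three: "number of perclose devices, LOS, and serum creatinine), Mann-Whitney U tests will be performed to compare the two treatment arms". The reporting is by arm: "Medians and interquartile ranges will be reported and interpreted for the non-parametric analyses of the count and continuous parameters". No between-arm estimate or confidence interval is promised for creatinine, although odds ratios with intervals are promised for the categorical secondary outcomes.

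Baseline adjustment appears once in section 9.2. It covers only characteristics found to differ significantly, and only one analysis: "differences at baseline will be accounted for in the primary analysis using logistic regression".

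Elsewhere the variable is described in two ways. The secondary objective in section 3.2.2 is "Examine renal function post procedure", and the list in section 4.2 records "Renal function lab results post procedure". Section 7.1 instead looks for clinical deterioration, including "drop in hemoglobin, worsening of creatinine, development of hypotension/shock". Section 4.2 also lists "Review of pre procedure laboratory results", without naming creatinine. No section gives a time point for the post-procedure value. Section 11.2 adds: "Any missing data will be omitted from the final statistical analysis".

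**The concern.** A patient's creatinine after the procedure is likely to depend on the value before it. A test on the post-procedure level alone treats the stable differences between patients as noise. With 50 per arm, that noise could hide a renal difference that the same patients' data might show. The pre-procedure value seems to be in hand already: pre-procedure laboratory results are reviewed, and worsening cannot be judged without an earlier value. At stake is the precision of one of eleven secondary objectives.

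**Working it through.** **Which variable is tested.** Sections 3.2.2 and 4.2 refer to renal function after the procedure, and section 9.2 says only serum creatinine. Together they point to the post-procedure level. The wording on worsening in section 7.1 points to change. Both readings are worked below.

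**Inputs from the documents.** 50 per arm and a two-tailed hypothesis (section 9.1, stated for the primary outcome); alpha 0.05 (section 9.2). The plan gives no power figure for creatinine, so there is none to reproduce.

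**Assumptions.** Log-normal creatinine with equal pre and post log SD of 0.4; a uniform 15% rise in one arm; pre/post correlation r from 0 to 0.9. The documents give none of these.

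**Formulas.**
- Effect on the log scale: ln(1.15) = 0.140. Unadjusted SE: 0.4 × √(2/50) = 0.08.
- Variance of the adjusted comparison relative to the unadjusted one, including the cost of the covariate: V = (1 − r²) × (1 + 1/(100 − 4)).
- Equivalent unadjusted total N: 100/V.
- Approximate power of the adjusted model: Φ(0.140/(0.08 × √V) − 1.96). At r = 0.7, V = 0.51 × 1.0104 = 0.515 and √V = 0.718, so power is Φ(2.43 − 1.96) = Φ(0.47) = 0.68.
- 95% CI factor for the geometric mean ratio: exp(1.985 × 0.08 × √(1 − r²)), where 1.985 is the t quantile on 97 df.

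**Results.** Power by simulation, 20,000 trials per setting, rounded:

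| r | V | Equivalent N | Mann-Whitney, level | Log ANCOVA | Rank ANCOVA | Mann-Whitney, log change | Adjusted CI factor |
|---|---|---|---|---|---|---|---|
| 0 | 1.01 | 99 | 39% | 41% | 39% | – | 1.17 |
| 0.3 | 0.92 | 109 | 39% | 43% | 42% | 30% | 1.16 |
| 0.5 | 0.76 | 132 | 39% | 51% | 48% | 39% | 1.15 |
| 0.7 | 0.52 | 194 | 39% | 68% | 63% | 59% | 1.12 |
| 0.8 | 0.36 | 275 | 39% | 82% | 77% | 76% | 1.10 |
| 0.9 | 0.19 | 521 | 39% | 98% | 96% | 97% | 1.07 |

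Type I error was close to 5% for all four tests. The unadjusted CI factor on the log scale is 1.17, so the interval narrows little at r = 0.5. At r = 0 adjustment loses nothing in power.

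**Other assumptions** (r = 0.5/0.7/0.8/0.9):
- Log SD 0.3: level test 61%; log ANCOVA 75/90/97/100%.
- Log SD 0.5: level test 27%; log ANCOVA 35/49/63/89%.
- Log SD 0.4, creatinine doubling in 25% against 5% of patients: level test 27%; log ANCOVA 37/46/53/64%; rank ANCOVA 32/39/44/55%.

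**If change is meant.** Log ANCOVA gains 51 − 39 = 12, 68 − 59 = 9, 82 − 76 = 6 and 98 − 97 = 1 points at r = 0.5/0.7/0.8/0.9. The gain equals that over the level test at r = 0.5 and is smaller above it. Below 0.5 the change score is the weaker choice: 30% against 39% for the level at r = 0.3.

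**Cost of omitting missing data.** A missing post-procedure value removes the patient from every test, so only a missing baseline is an extra loss. Assume 20% lack a baseline, at random and equally in both arms, leaving 40 per arm. The comparator is the level test in all 50, at 39%.
- r = 0.3: log ANCOVA about 36%, rank ANCOVA about 35%. The gain is gone.
- r = 0.5: log ANCOVA 42%, rank ANCOVA 40%. The gain is nearly gone for the first and gone for the second.
- r = 0.7: log ANCOVA 57%, rank ANCOVA 53%. Much of the gain remains.

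At 30% missing, log ANCOVA gives 38% at r = 0.5 and 51% at r = 0.7.

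**The case against.** The strongest reply is that section 9.2 does not say which creatinine variable is tested. If it means change, the pre-procedure value is already used. This stands: the loss of precision against the level test is conditional on one reading, and a reader who infers that the plan certainly ignores baseline goes further than the text.

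A second reply is that the gain depends on a correlation that no document gives, and on complete baseline values when missing data are to be omitted. This also stands. At r = 0.3 the gain is about 4 points even with complete data, and a modest share of missing baselines removes it. The documents do not say how complete the pre-procedure values will be, or that creatinine is among them.

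A third reply is that a rank test is a reasonable choice for a skewed laboratory value in a pilot with no power claim for it. That is fair as a defence of validity. It does not count against adjustment: a log model accommodates this kind of skew, and a pilot gains from an effect estimate with an interval, which the plan does not promise for creatinine.

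A reader might infer that the unadjusted comparison is biased, or that chance baseline imbalance makes it invalid. The documents do not support that. Patients are randomised, and the test holds its type I error.

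**Conclusion.** The point holds as a conditional, minor loss of precision. If the post-procedure level is tested, the planned test has about 39% power under the assumed 15% rise and log SD of 0.4. Adjustment on the log scale would raise this by about 4 points at r = 0.3, 12 at r = 0.5 and 29 at r = 0.7, given complete baseline values. If change is tested, the gain is about 1 to 12 points for r between 0.5 and 0.9. All of these figures rest on assumed SD, effect and correlation. Under either reading, the variable and its timing need to be defined. The primary analysis is untouched, and nothing here questions the validity of the planned test. This is a cheap improvement to one secondary outcome.

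**What to change.** In section 9.2:

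1. Prespecify one main analysis for creatinine: a linear model of log post-procedure creatinine on arm and log pre-procedure creatinine, fitted whatever the baseline significance tests show. Report the adjusted ratio of geometric means with its 95% CI.
2. Define baseline as the last pre-procedure value, and the outcome as the value in a named post-procedure window that matches routine draws. A window, rather than a single fixed time, limits the loss of discharged patients.
3. Keep the planned Mann-Whitney test, or a rank ANCOVA, as a fixed sensitivity analysis. Do not make the choice of method depend on a check of log-normality.
4. Report the number of patients per arm with both values, because section 11.2 omits missing data.

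The cost is two or three sentences and a little analysis work. No new data are needed if the pre-procedure laboratory results include creatinine and the window fits routine draws. The downside is that patients without a pre-procedure value also drop out of the adjusted analysis.
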